10. TRIAL PROCEDURES AND ASSESSMENTS

The Study Calendar (Section 9) summarizes the trial procedures to be performed at each visit. Individual trial procedures are described in detail below. It may be necessary to perform these procedures at unscheduled time points if deemed clinically necessary by the investigator.

Furthermore, additional evaluations/testing may be deemed necessary by the Sponsor for reasons related to participant safety. In some cases, such evaluation/testing may be potentially sensitive in nature (e.g., HIV, Hepatitis C, etc.), and thus local regulations may require that additional informed consent be obtained from the participant. In these cases, such evaluations/testing will be performed in accordance with those regulations.

10.1 Administrative Procedures

10.1.1 Informed Consent

The Investigator must obtain documented consent from each potential participant prior to participating in a clinical trial.

10.1.2 General Informed Consent

Consent must be documented by the participant's dated signature or by the participant's legally acceptable representative's dated signature on a consent form along with the dated signature of the person conducting the consent discussion.

A copy of the signed and dated consent form should be given to the participant before participation in the trial.

The initial informed consent form, any subsequent revised written informed consent form and any written information provided to the participant must receive the IRB/ERC's approval/favorable opinion in advance of use. The participant or his/her legally acceptable representative should be informed in a timely manner if new information becomes available that may be relevant to the participant's willingness to continue participation in the trial. The communication of this information will be provided and documented via a revised consent form or addendum to the original consent form that captures the participant's dated signature or by the participant's legally acceptable representative's dated signature.

Specifics about a trial and the trial population will be added to the consent form template at the protocol level.

The informed consent will adhere to IRB/ERC requirements, applicable laws and regulations and Sponsor requirements.

10.1.3 Inclusion/Exclusion Criteria

All inclusion and exclusion criteria will be reviewed by the investigator or qualified designee to ensure that the participant qualifies for the trial.

10.1.4 Medical History

A medical history will be obtained by the investigator or qualified designee. Medical history will include all active conditions, and any condition diagnosed within the prior 10 years that are considered to be clinically significant by the Investigator. Details regarding the disease for which the participant has enrolled in this study will be recorded separately and not listed as medical history.

10.2 Prior and Concomitant Medications Review

10.2.1 Prior Medications

The investigator or qualified designee will review prior medication use, including any protocol-specified washout requirement, and record prior medication taken by the participant within 28 days before starting the trial. Treatment for the disease for which the participant has enrolled in this study will be recorded separately and not listed as a prior medication.

10.2.2 Concomitant Medications

The investigator or qualified designee will record medication, if any, taken by the participant during the trial. All medications related to reportable SAEs and ECIs should be recorded as defined in Section 6.

10.3 Disease Details and Treatments

10.3.1 Disease Details

The investigator or qualified designee will obtain prior and current details regarding disease status.

10.3.1.1 Prior Treatment Details

The investigator or qualified designee will review all prior cancer treatments including systemic treatments, radiation and surgeries.

10.3.1.2 Subsequent Anti-Cancer Therapy Status

The investigator or qualified designee will review all new anti-neoplastic therapy initiated after the last dose of trial treatment. If a participant initiates a new anti-cancer therapy within 30 days after the last dose of trial treatment, the 30 day Safety Follow-up visit must occur before the first dose of the new therapy. Once new anti-cancer therapy has been initiated the participant will move into survival follow-up.

10.3.1.3 Assignment of Screening Number

All consented participants will be given a unique screening number that will be used to identify the participant for all procedures that occur prior to randomization or treatment allocation. Screening numbers will be assigned and maintained by the clinical research coordinator at the lead site. Each participant will be assigned only one screening number. Screening numbers must not be re-used for different participants. Any participant who is screened multiple times will retain the original screening number assigned at the initial screening visit.

10.3.1.4 Trial Compliance (Medications)

Interruptions from the protocol specified treatment plan for 12 weeks between doses due to toxicity require consultation between the investigator and the Sponsor and written documentation of the collaborative decision on participant management. Administration of trial medications will be witnessed by the investigator and/or trial staff. The total volume of trial treatments infused will be compared to the total volume prepared to determine compliance with each dose administered. The instructions for preparing and administering pembrolizumab and trebananib are provided in the Investigational Product Instruction Manual.

10.3.2 Clinical Procedures/Assessments

10.3.2.1 Adverse Event (AE) Monitoring

The investigator or qualified designee will assess each participant to evaluate for potential new or worsening AEs as specified in the Trial Flow Chart and more frequently if clinically indicated. Adverse experiences will be graded and recorded throughout the study and during the follow-up period according to NCI CTCAE Version 4.0. Toxicities will be characterized in terms regarding seriousness, causality, toxicity grading, and action taken with regard to trial treatment.

Please refer to section 6 for detailed information regarding the assessment and recording of AEs.

10.3.2.2 Physical Exam

The investigator or qualified designee will perform a physical exam during the screening period. Clinically significant abnormal findings should be recorded as medical history. A physical exam should be performed during screening, prior to the administration of each dose of trial treatment and as specified in the Trial Flow Chart (Section 9).

10.3.2.3 Vital Signs

The investigator or qualified designee will take vital signs at screening, prior to the administration of each dose of trial treatment and at treatment discontinuation as specified in the Trial Flow Chart (Section 9). Vital signs should include temperature, pulse, respiratory rate, weight and blood pressure. Height will be measured at screening only.

10.3.2.4 Eastern Cooperative Oncology Group (ECOG) Performance Scale

The investigator or qualified designee will assess ECOG status at screening, prior to the administration of each dose of trial treatment and discontinuation of trial treatment as specified in the Trial Flow Chart. Please refer to Appendix A.

10.3.2.5 Laboratory Tests for Hematology, Chemistry, Urinalysis, and other laboratory tests

Laboratory tests for hematology, chemistry, urinalysis, and others are specified in Table 14

Pre-dose laboratory procedures can be conducted up to 72 hours prior to dosing with the exception of the urine pregnancy test for women of child bearing potential (which must be performed within 24 hours prior to dosing). Results must be reviewed by the investigator or qualified designee and found to be acceptable prior to each dose of trial treatment.

Table 14. Laboratory Tests

Hematology	Chemistry	Urinalysis	Other
Hematocrit	Albumin	Blood	Serum β -human chorionic gonadotropin
Hemoglobin	Alkaline phosphatase	Glucose	(β -hCG)
Platelet count	Alanine aminotransferase (ALT)	Protein	PT (INR)
WBC (total and differential)	Aspartate aminotransferase (AST)	Specific gravity	aPTT
Red Blood Cell Count	Lactate dehydrogenase (LDH)	Microscopic exam (If abnormal)	Total triiodothyronine (T3)
Absolute Neutrophil Count	Carbon Dioxide	results are noted	Free thyroxine (T4)
Absolute Lymphocyte Count	(CO_2 or biocarbonate)	Urine pregnancy test	Thyroid stimulating hormone (TSH)
	Uric Acid	Creatinine	
	Calcium		
	Chloride		Blood for correlative studies
	Glucose		
	Phosphorus		CEA for colorectal participants
	Potassium		CA125 for ovarian participants
	Sodium		
	Magnesium		
	Total Bilirubin		
	Direct Bilirubin (If total bilirubin is elevated above the upper limit of normal)		
	Total protein		
	Blood Urea Nitrogen		
	Lipase		
	Amylase		

10.4 Other Procedures

10.4.1 Screening

The informed consent form must be signed prior to completing any protocol-specified procedure. Within 28 days prior to registration (except where noted below), potential participants will be evaluated to determine if they fulfill the entry requirements as set forth in Section 5.1. Screening procedures may be repeated after consultation with the Sponsor. After providing consent, participants will be assigned a screening number. Results of a test performed prior to the participant signing consent as part of routine clinical management are acceptable in lieu of a screening test if performed within the specified time frame. Exceptions to the 28-day screening window include the following assessments/tests:

- For women of reproductive potential, a urine pregnancy test will be performed within 24 hours prior to the first dose of trial treatment. If urine pregnancy results cannot be confirmed as negative, a serum pregnancy test will be required (performed by the local study site laboratory).

Participants may be rescreened after initially failing to meet the inclusion/exclusion criteria. Results from assessments performed during the initial screening period are acceptable in lieu of a repeat screening test if performed within the specified time frame and the inclusion/exclusion criteria is met.

10.4.2 Withdrawal/Discontinuation

When a participant discontinues/withdraws prior to trial completion, all applicable activities scheduled for the final trial visit should be performed at the time of discontinuation. Any adverse events which are present at the time of discontinuation/withdrawal should be followed in accordance with the safety requirements outlined in Section 6 – Adverse Events: List and Reporting Requirements. Participants who a) attain a CR or b) complete 24 months of treatment with pembrolizumab may discontinue treatment with the option of restarting treatment if they meet the criteria specified in Section 10.5.4. After discontinuing treatment following assessment of CR, these participants should return to the site for a Safety Follow-up Visit (described in Section 10.5.1) and then proceed to the Follow-Up Period of the study (described in Section 10.5.2).

10.5 Post Treatment Visits

10.5.1 Safety Follow-Up Visit

The mandatory Safety Follow-Up Visit should be conducted approximately 30 days after the last dose of trial treatment or before the initiation of a new anti-cancer treatment, whichever comes first. All AEs that occur prior to the Safety Follow-Up Visit should be recorded. Participants will be followed until the beginning of a new anti-neoplastic therapy. SAEs that occur within 90 days of the end of treatment or before initiation of a new anti-cancer treatment should also be

followed and recorded. Participants who are eligible for retreatment with pembrolizumab (as described in Section 10.5.4) may have up to two safety follow-up visits, one after the Treatment Period and one after the Second Course Phase.

10.5.2 Follow-Up Visits

Participants who discontinue trial treatment for a reason other than disease progression will move into the Follow-Up Phase and should be assessed every 12 weeks (84 ± 7 days) by radiologic imaging to monitor disease status for at least 1 year. Every effort should be made to collect information regarding disease status until the start of new anti-neoplastic therapy, disease progression, death, end of the study or if the participant begins retreatment with pembrolizumab as detailed in Section 10.5.4. Information regarding post-study anti-neoplastic treatment will be collected if new treatment is initiated.

Participants who are eligible to receive retreatment with pembrolizumab according to the criteria in Section 11.3.4 will move from the follow-up phase to the Second Course Phase when they experience disease progression. Details are provided in Section 9 – Trial Flow Chart for Retreatment.

10.5.3 Survival Follow-Up

Once a participant experiences confirmed disease progression or starts a new anti-cancer therapy, the participant moves into the survival follow-up phase and should be contacted by telephone every 12 weeks (84 ± 7 days) to assess for survival status until death, withdrawal of consent, or the end of the study, whichever occurs first.

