5.3.3 Dose Modifications

5.3.3.1 Pembrolizumab Dose Modification and Toxicity Management for Immune-Related AEs Associated with Pembrolizumab and Combination Therapy

AEs associated with pembrolizumab exposure, including coadministration with additional compounds, may represent an immunologic etiology. These immune-related AEs (irAEs) may occur shortly after the first dose or several months after the last dose of pembrolizumab/combination treatment and may affect more than one body system simultaneously. Therefore, early recognition and initiation of treatment is critical to reduce complications. Based on existing clinical study data, most irAEs were reversible and could be managed with interruptions of pembrolizumab/combination treatment, administration of corticosteroids and/or other supportive care. For suspected irAEs, ensure adequate evaluation to confirm etiology or exclude other causes. Additional procedures or tests such as bronchoscopy, endoscopy, skin biopsy may be included as part of the evaluation. Dose modification and toxicity management guidelines for irAEs associated with pembrolizumab/combination treatment are provided in Table 5.. See Section 5.9 for supportive care guidelines, including use of corticosteroids.

Attribution of Toxicity:

When study interventions are administered in combination, attribution of an adverse event to a single component is likely to be difficult. Therefore, while the investigator may attribute a toxicity event [to the combination, to [trebananib alone] or to pembrolizumab alone], for adverse events listed in Table 5, both interventions must be held according to the criteria in Table 5 Dose Modification and Toxicity Management Guidelines for Immune-Related Adverse Events Associated with Pembrolizumab.

Holding Study Interventions:

When study interventions are administered in combination, if the AE is considered immune-related, both interventions should be held according to the recommended dose modifications.

Restarting Study Interventions:

Participants may not have any dose modifications (no change in dose or schedule) of pembrolizumab in this study, as described in Table 5.

- If the toxicity does not resolve or the criteria for resuming treatment are not met, the participant must be discontinued from all study interventions
- If the toxicities do not resolve and conditions are aligned with what is defined in Table 5, the combination of trebananib and pembrolizumab may be restarted at the discretion of the

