5.13 End of Treatment Evaluation and Follow-Up

The End of Treatment and Follow-up visit procedures are listed in Section 9 (Protocol Flow Chart) and Section 11 (Visit Requirements). After the end of treatment, each participant will be followed for 30 days for adverse event monitoring (serious adverse events will be collected for 90 days after the end of treatment as described in Section 6).

Participants who discontinue for reasons other than progressive disease will have post-treatment follow-up for disease status until disease progression, initiating a non-study cancer treatment, withdrawing consent or becoming lost to follow-up.

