From the time of cycle 1 day 1 through 30 days following cessation of treatment, all adverse events must be reported by the investigator. Such events will be recorded at each examination on the Adverse Event case report forms/worksheets. The reporting timeframe for adverse events meeting any serious criteria is described in section 6.3 The investigator will make every attempt to follow all participants with non-serious adverse events for outcome.

Adverse events will not be collected for participants during the pre-screening period (for determination of archival tissue status) as long as that participant has not undergone any protocol-specified procedure or intervention.

6.1 Definition of an Overdose for Pembrolizumab and Reporting of Overdose to the Sponsor and to Merck

For purposes of this trial, an overdose of pembrolizumab will be defined as any dose of 1,000 mg or greater (≥ 5 times the indicated dose). No specific information is available on the treatment of overdose of pembrolizumab. Appropriate supportive treatment should be provided if clinically indicated. In the event of overdose, the participant should be observed closely for signs of toxicity. Appropriate supportive treatment should be provided if clinically indicated.

If an adverse event(s) is associated with (“results from”) the overdose of a Merck product, the adverse event(s) is reported as a serious adverse event, even if no other seriousness criteria are met.

If a dose of Merck’s product meeting the protocol definition of overdose is taken without any associated clinical symptoms or abnormal laboratory results, the overdose is reported as a non-serious Event of Clinical Interest (ECI), using the terminology “accidental or intentional overdose without adverse effect.”

All reports of overdose with and without an adverse event must be reported within 24 hours to the IND holder and within 2 working days to Merck Global Safety. (Attn: Worldwide Product Safety; [contact])

6.2 Reporting of Pregnancy and Lactation to the Sponsor and to Merck and Amgen

Although pregnancy and lactation are not considered adverse events, it is the responsibility of investigators or their designees to report any pregnancy or lactation in a participant (spontaneously reported to them) that occurs during the trial.

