6.3 Immediate Reporting of Adverse Events to the Sponsor and to Merck

6.3.1 Serious Adverse Events

A serious adverse event is any adverse event occurring at any dose or during any use of Merck or Amgen products that:

- Results in death;
- Is life threatening;
- Results in persistent or significant disability/incapacity;
- Results in or prolongs an existing inpatient hospitalization;
- Is a congenital anomaly/birth defect;
- Is another important medical event

- **Note:** In addition to the above criteria, adverse events meeting either of the below criteria, although not serious per ICH definition, are reportable to the Sponsor, Merck and Amgen in the same timeframe as SAEs to meet certain local requirements. Therefore, these events are considered serious by Merck and Amgen for collection purposes.
 - Is a new cancer (that is not a condition of the study);
 - Is associated with an overdose.

For the time period beginning when the consent form is signed until the participant presents for cycle 1 day 1, any serious adverse event that occurs to any participant must be reported within 24 hours to the IND holder and within 2 working days to Merck Global Safety and Amgen ONLY if it causes the participant to be excluded from the trial, or is the result of a protocol-specified intervention, including but not limited to washout or discontinuation of usual therapy, diet, placebo treatment or a procedure.

Any serious adverse event, or follow up to a serious adverse event, including death due to any cause other than progression of the cancer under study that occurs to any participant from the time the participant presents for Cycle 1 Day 1 through 90 days following cessation of treatment, or the initiation of new anti-cancer therapy, whichever is earlier, whether or not related to Merck or Amgen product, must be reported within 24 hours to the Sponsor and within 2 working days to Merck Global Safety and Amgen. Additionally, any serious adverse event, considered by an investigator who is a qualified physician to be related to Merck product that is brought to the attention of the investigator at any time following consent through the end of the specified safety follow-up period specified in the paragraph above, or at any time outside of the time period specified in the previous paragraph also must be reported immediately to the IND holder and to Merck Global Safety.

All participants with serious adverse events must be followed up for outcome.

[REDACTED]

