6.3.7 Events of Clinical Interest for Pembrolizumab

Selected non-serious and serious adverse events are also known as Events of Clinical Interest (ECI) and must be reported within 24 hours to the IND holder and within 2 working days to Merck Global Safety. [REDACTED]

For the time period beginning when the consent form is signed until the participant presents for cycle 1 day 1, any ECI, or follow up to an ECI, that occurs to any participant must be reported within 24 hours to the Sponsor and within 2 working days to Merck Global Safety ONLY if it causes the participant to be excluded from the trial, or is the result of a protocol-specified intervention, including but not limited to washout or discontinuation of usual therapy, diet, placebo treatment or a procedure.

For the time period beginning when the participant presents for cycle 1 day 1 through 90 days following cessation of treatment, or 30 days following cessation of treatment if the participant initiates new anticancer therapy, whichever is earlier, any ECI, or follow up to an ECI, whether or not related to Merck product, must be reported within 24 hours to the Sponsor and within 24 hours to Merck Global Safety.

Events of clinical interest for this trial include:

1. An overdose of Merck product., as defined in Section 6.1 - Definition of an Overdose for This Protocol and Reporting of Overdose to the Sponsor, that is not associated with clinical symptoms or abnormal laboratory results.
2. An elevated AST or ALT lab value that is greater than or equal to 3X the upper limit of normal and an elevated total bilirubin lab value that is greater than or equal to 2X the upper limit of normal and, at the same time, an alkaline phosphatase lab value that is less than 2X the upper limit of normal, as determined by way of protocol-specified laboratory testing or unscheduled laboratory testing.*

*Note: These criteria are based upon available regulatory guidance documents. The purpose of the criteria is to specify a threshold of abnormal hepatic tests that may require an additional evaluation for an underlying etiology.

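### After progression, no scheduled contact asks about serious adverse events from about day 30 to day 90, so late serious events may be under-ascertained in a way that depends on tumor outcome

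*Combined protocol and SAP*

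**What the plan says.** **The duty to collect.** For adverse events in general, Section 6 states: "From the time of cycle 1 day 1 through 30 days following cessation of treatment, all adverse events must be reported by the investigator". For SAEs the period is longer. Section 5.13 says that "serious adverse events will be collected for 90 days after the end of treatment as described in Section 6", and Section 6.3.1 gives the full rule: "through 90 days following cessation of treatment, or the initiation of new anti-cancer therapy, whichever is earlier". Section 10.5.1 repeats the 90-day SAE period. Events of clinical interest (ECIs) are due "through 90 days following cessation of treatment, or 30 days following cessation of treatment if the participant initiates new anticancer therapy, whichever is earlier" (Section 6.3.7). The closing paragraph of Section 6.4 gives a third period, which ends safety reporting 70 days after the last dose.

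**The schedule.** In the post-treatment calendar of Section 9, the adverse event review row is marked at the End of Treatment visit, the Safety Follow-up at 30 ± 3 days, and the Follow Up Visits. It is blank under Survival Follow-Up, where only survival status and post-study therapy are listed. Section 10.5.2 decides who attends the Follow Up Visits: "Participants who discontinue trial treatment for a reason other than disease progression will move into the Follow-Up Phase". Under Section 10.5.3, patients with confirmed progression or new therapy instead "should be contacted by telephone every 12 weeks (84 ± 7 days) to assess for survival status". Section 5.14 also describes contact after progression as serving overall survival, by telephone or record review.

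**The risk.** Section 5.3.3.1 says that immune-related events "may occur shortly after the first dose or several months after the last dose of pembrolizumab/combination treatment".

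**The concern.** The plan sets a 90-day SAE period and names delayed immune-related events as a reason to look late. It then sends one group of patients to a contact that does not ask about them. Patients who stop for other reasons are asked at their 12-week visit. Ascertainment of late SAEs therefore differs by tumor outcome.

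Safety and tolerability are the primary objective of both parts of the trial (Section 1.2). Section 14.7 also halts expansion enrollment for review when two or more late treatment-related toxicities are observed. With a threshold of two, a single unrecorded event could decide whether that review takes place.

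**Working it through.** The plan states no figure to reproduce here. The check sets the collection windows against the visit schedule. I treat last dose, cessation of treatment and discontinuation as the same day, because the sections count from different ones of these.

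**1. Last review scheduled for every patient.** The Safety Follow-up is at 30 ± 3 days, so 30 − 3 = day 27 to 30 + 3 = day 33. If new therapy starts within 30 days, the visit is brought forward to precede it (Sections 10.3.1.2 and 10.5.1). The SAE window then closes with the new therapy, and those patients have no gap.

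**2. Next contact, by reason for stopping.**

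| | Other reason | Confirmed progression |
|---|---|---|
| Phase | Follow-Up (10.5.2) | Survival Follow-Up (10.5.3) |
| First contact | 84 ± 7: days 77 to 91 | 84 ± 7: days 77 to 91, if counted from discontinuation |
| Adverse event review in calendar | Yes | No |

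**3. Length of the gap for a progressor without new therapy.** 90 − 33 = 57 days to 90 − 27 = 63 days. If new therapy starts before day 90, the gap ends on that date.

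**4. Size of the difference between groups.** A patient in the Follow-Up Phase is also not seen between about day 30 and days 77 to 91. That visit looks back over the interval, however, and leaves at most 90 − 77 = 13 days of the window unreviewed. The difference is one retrospective query.

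**5. What the documents say about numbers.**
- Section 14.8 expects about 40% to complete 24 weeks. 0.40 × 48 = 19.2, which agrees with its 19 to 20 patients. The other 28.8 of 48 (60%) stop earlier, for any reason.
- Section 14.2 reports 1 partial response and 4 with stable disease among 15 colorectal patients. 15 − 1 − 4 = 10, and 10/15 = 67%, with an exact 95% confidence interval of 38% to 88%.

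Neither figure counts patients who stop for progression, and neither says how many of those start new therapy before day 90.

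**6. Illustration on assumed inputs.** Suppose 40% to 80% of the 60 patients stop for progression, and 1% to 10% of them have a serious event between days 30 and 90.
- Low end: 60 × 0.40 × 0.01 = 0.24 events.
- High end: 60 × 0.80 × 0.10 = 4.8 events.

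These are events that would rely on unscheduled reporting, not events missed. Within these assumptions they are upper bounds, because the SAE window closes when new therapy starts.

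**The case against.** The strongest reply is that the duty to collect already covers progressors. Section 6.3.1 requires any SAE in any participant, related or not, to be reported within 24 hours up to day 90 or new therapy. SAEs related to pembrolizumab are reportable at any time. Section 10.5.1 has SAEs within 90 days followed and recorded, with no exception for progression. Section 5.12 keeps patients who stop early in study visits and procedures, and the calendar heading for the Follow Up Visits carries no exclusion. Section 5.14 allows record review, which can reveal a hospitalization.

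This shows that SAE reporting does not lapse, and that a late event can still be found without the patient volunteering it. It does not supply a scheduled query. A duty to report acts only once the investigator knows of the event, and the record review is described as being for survival. The specific routing in Sections 10.5.2 and 10.5.3 takes progressors away from the visit that has the review. If Section 5.12 was meant to override that routing, the sections conflict and need correcting anyway.

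Two further objections stand as limits:
- The gap exists only until new therapy starts.
- ECIs add almost nothing. The list introduced by "Events of clinical interest for this trial include" in Section 6.3.7 has two items: overdose without symptoms, and one pattern of liver tests. The first cannot newly arise after the last dose, and a telephone question cannot detect the second. Other non-serious events are by design collected only to day 30. The point rests on SAEs.

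**Conclusion.** The schedule, followed as written, gives progressors not yet on new therapy no adverse event review after about day 30, although their SAEs are due to day 90. Late serious immune-related events in these patients depend on unscheduled reporting and may be under-ascertained, and whether a patient is asked depends on tumor outcome. The gap is 57 to 63 days at most, and the contrast with other patients is one query near week 12. This assumes that sites follow Sections 10.5.2 and 10.5.3 rather than the broader statement in Section 5.12.

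A reader might infer more, but the documents do not support it:
- **That late events are missed in most patients.** No section gives the share who stop for progression. The interval around 10 of 15 includes one half, and a patient without a scheduled query is not a patient with a missed event.
- **That late-toxicity counts will be too low.** Under-ascertainment is possible but not shown. Section 14.7 does not define late, so events during later treatment cycles, which are reviewed every cycle, may also count toward it.
- **That two-thirds of the window is lost for every progressor.** This ignores its closure at new therapy.

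The number of patients or events affected cannot be computed from the documents. The gap should still be closed, because it bears on the primary objective and the remedy is small.

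**What to change.** In the Section 9 calendar and in Section 10.5.3, add two items to the first Survival Follow-Up contact: an SAE review covering the period to day 90 or new therapy, and the start date of any new anti-cancer therapy. Time that contact at or just after day 90 from the last dose, for example day 90 to 97, so that one call closes the window. The current call can fall as early as day 77 and would usually precede day 90. The start date shows when the SAE window closed for each patient.

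Apply this to patients in survival follow-up only. Patients in the Follow-Up Phase should keep their 12-week visit with its existing review; a day-90 call would be an additional contact for them. If progressors were meant to attend the Follow Up Visits, Sections 10.5.2 and 10.5.3 should say so instead.

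In the same edit, reconcile the 70-day safety reporting period in Section 6.4 with the 30-day adverse event and 90-day SAE windows.

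The cost is small. The earliest date of the first survival call moves from day 77 to day 90 (13 days), the latest from day 91 to day 97 (6 days), and there is slightly more SAE paperwork. No visit or procedure is added.
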